Title: Postoperative Activity Restrictions in Children (PARC)

NCT04145895

Protocol approval date: 10/29/2021

Title: Postoperative Activity Restrictions in Children (PARC)

Principal Investigator: [name]

NCT04145895

Protocol approval date: 10/29/2021

IRB# 2019-224

SUMMARY

BACKGROUND: Currently, there are no evidence-based guidelines for postoperative activity restrictions in routine pediatric surgery. Recent studies suggest that patients may return to normal activity earlier than previously thought. We aim to compare time to full activity and post-operative outcomes. This study will describe family preferences for self-directed activity restrictions (SDAR) and physician directed activity restrictions (PDAR) following routine surgeries.

STUDY DESIGN: Single institution, prospective clinical trial (NCT04145895). Patients who present for a routine inguinal hernia repair or laparoscopic appendectomy for uncomplicated appendicitis are eligible for participation. Participating families will choose to enroll in either the control (PDAR) or experimental (SDAR) groups. The PDAR patients are restricted from full activity for two weeks post-operatively. For SDAR, patients are instructed to return to full activity when pain is improving and the family feels comfortable. At 4-6 weeks postoperatively, caregivers will complete a survey to assess time to resume full activity, time to return to school and work, surgical complications, and patient and caregiver satisfaction.

BACKGROUND AND SIGNIFICANCE

Postoperative activity restrictions (PAR) serve to minimize the risk of complications and prevent stress on the operative site following abdominal surgery. By minimizing intra-abdominal pressure, PAR are used to prevent the breakdown of the surgical repair and closure.¹ Commonly restricted activities include heavy lifting, exercise, and strenuous activity. As children are highly active by nature, limiting physical activity is difficult.² Pediatric surgeons may restrict time to return to school or extracurricular activities. However, these restrictions create a societal burden through school absences and missed work days. Additionally, PAR can negatively impact a child's psychosocial well-being and cause undue family stress.²

[figure not shown]
PAR are physician-dependent as evidence-based guidelines for restrictions following routine pediatric surgery are not established. Recent studies demonstrate considerable variability in surgeons' recommendations following laparoscopic appendectomy and inguinal hernia repair in children.¹ The lack of consensus amongst physicians may be attributed to the corresponding lack of evidence in this area.³ A 2020 survey on surgeon recommendations for postoperative activity found that only 23.8% of respondents indicated that their recommendations were based on evidence in the literature.⁴ More than half of the respondents indicated that they followed practices learned in training, and 50.7% indicated that recommendations had been developed from previous experience.⁴ Others propose the use of self-directed activity restrictions (SDAR) following routine pediatric surgery.² Proponents of SDAR suggest patients may safely return to normal activity earlier than previously thought. Additional benefits include greater patient and family satisfaction and quality of life.

Prospective investigation is needed to develop evidence-based guidelines for PAR in the pediatric population. We conducted a single institution, prospective clinical trial (NCT04145895) to compare length of time to full activity, as well as, post-operative outcomes of SDAR and physician directed activity restrictions (PDAR) in children following inguinal hernia repair and laparoscopic appendectomy. Further, we aimed to describe the preference of families for SDAR or PDAR, patient and caregiver satisfaction, and parental time of work. This paper reports the preliminary results of this study.

METHODS

Participants

This study was approved by the Beaumont Institutional Review Board (2019-224). Patients who presented to Beaumont Royal Oak and Beaumont Troy for a routine inguinal hernia repair (ages 2-13 years) or laparoscopic appendectomy for uncomplicated appendicitis (ages 0-17 years) were eligible for participation. Patients meeting eligibility criteria (**Figure 1**) were identified by the pediatric surgeons, including the Primary Investigator ([name]), and were provided with an information sheet detailing the study, which served as consent for participation. Parents and patients who elected to participate then chose to enroll in the control group (PDAR) or experimental group (SDAR). The PDAR instructions detailed that patients are restricted from full, normal activity for 2 weeks after their procedure. The SDAR instructions specified that they may return to full activity when their pain is improving and the parent, or guardian, feels comfortable advancing their activity. Enrollment is still accruing for this study.

Figure 1. Patient eligibility criteria**Figure 1.** Patient eligibility criteria for participation in the clinical trial.

Data Collection

Baseline characteristics, comorbidities, surgical complications, length of stay, and pain medications will be obtained for each participant from the time of surgery. At 4-6 weeks postoperatively, parents or guardians will be asked to complete a survey at their follow-up appointment or online using Research Electronic Data Capture (REDCap). The survey includes assessments of the time taken to return to school and work, return to full activity, surgical complications, and patient and caregiver satisfaction (**Figure 2**).

Figure 2. Postoperative Survey

Your Child's Experience Postoperatively	
For how long was your child on pain medications following the procedure?	 1-2 days  3-4 days  4-7 days  >1 week
How many days following the procedure did your child return to school, daycare, summer camp, or summer school?	
Approximately how many days after surgery did your child return to full activity (sports, gym, dance, outdoor play, etc.)?	
Did your child's wound have any oozing or bleeding following discharge from the hospital?	 None  Mild (slight drainage)  Moderate (drainage with blood)  Severe (oozing with blood)
If you answered mild, moderate, or severe to the previous question, when did this occur?	
If you answered mild, moderate or severe to the previous question, did this require any treatment by your surgical team?	
Did your child experience any postoperative complications?	 No  Yes
If you answered yes to the previous question, please specify:	
After resuming full activity, did your child experience an increase in pain?	 No  Yes
If you answered yes to the previous question, did they require any medication for the pain?	 No  Yes
How compliant was your child with their postoperative instructions?	 Compliant  Partially compliant  Not compliant

Postoperative Activity Restrictions in Children After Routine Surgery

5

How would you describe your child's overall satisfaction following the procedure?	 Very satisfied  Satisfied  Neither satisfied or dissatisfied  Dissatisfied  Very dissatisfied
Your Experience Postoperatively	
What is your relationship to the child?	 Mother  Father  Grandparent  Legal Guardian  Other
Did you or another caregiver take time off work to care for your child following their procedure?	 Yes  No
Did you have to find additional childcare for your child following their procedure?	 Yes  No
How would you describe your overall satisfaction following your child's procedure?	 Very satisfied  Satisfied  Neither satisfied or dissatisfied  Dissatisfied  Very dissatisfied
Were you satisfied with the instructions detailed in your discharge guidelines?	 Very satisfied  Satisfied  Neither satisfied or dissatisfied  Dissatisfied  Very dissatisfied
If your followed physician-directed instructions, did you follow the recommendations strictly?	 Yes  No  Somewhat
If you chose self-directed instructions, did you feel comfortable determining when your child was able to resume full activity?	 I felt comfortable  I had some concerns  I did not feel comfortable

Figure 2. Postoperative survey provided to patients 4-6 weeks following their procedure. Patients were able to complete the survey at their postoperative visit or online via REDCap.
	

Objectives

The primary outcome of this study is length of time to full activity.

Secondary outcomes will evaluate patient preference to PDAR and SDAR based on choice of study arm and the impact of restriction type on number of parental days off work.

Clinical complications will also be tracked. Patient satisfaction will be defined as a cumulative score of three satisfaction factors (child, parent, and satisfaction with discharge guidelines).

Statistical Analysis

Continuous data will be presented as mean (SD) or median (IQR) depending on distribution, and analyzed using unpaired t tests or Mann Whitney ranked sum tests. Categorical data will be presented as number (%) and will be analyzed using Chi Square or Fisher's exact test depending on frequencies P values <.05 will be considered significant.

REFERENCES

3. Pommergaard H-C, Burcharth J, Danielsen A, Angenete E, Haglind E, Rosenberg J. No consensus on restrictions on physical activity to prevent incisional hernias after surgery. *Hernia*. 2014;18(4):495-500. doi:10.1007/s10029-013-1113-8

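### No result by operation is specified, so the SDAR preference share depends on case mix and the unadjusted arm difference may describe neither hernia repair nor appendectomy

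*Combined protocol and SAP*

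**What the plan says.** Background and Significance gives the purpose as evidence for paediatric guidelines and sets the SDAR-PDAR comparison "in children following inguinal hernia repair and laparoscopic appendectomy". Methods, Participants, admits the two operations over different age ranges: "routine inguinal hernia repair (ages 2-13 years) or laparoscopic appendectomy for uncomplicated appendicitis (ages 0-17 years) were eligible for participation". Families choose their arm. One two-week PDAR rule and one SDAR instruction cover both operations.

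Under Objectives, "The primary outcome of this study is length of time to full activity". On preference, "Secondary outcomes will evaluate patient preference to PDAR and SDAR based on choice of study arm". Under Statistical Analysis, continuous data are "analyzed using unpaired t tests or Mann Whitney ranked sum tests", and "Categorical data will be presented as number (%) and will be analyzed using Chi Square or Fisher's exact test".

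No stratum, covariate, subgroup or interaction by operation appears in the text. No target mix of operations, sample size, expected preference share or expected recovery time is given.

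**The concern.** The findings are meant to inform advice after two distinct operations, but the plan does not call for a figure for either one. Two outcomes are affected in different ways.

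- **Preference share.** This is a single proportion. If families' preferences differ by operation, it moves with the ratio of hernia repairs to appendectomies enrolled, even when nothing changes within either operation. Adjusting the arm comparison does not alter it; only a split by operation does.
- **Days to full activity.** Because families choose, the operation mix can differ between arms. The unadjusted difference then combines the effect of the instructions with any difference in recovery between the operations.

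The design also gives a reason why the effect might vary by operation. PDAR families are held to the same two weeks after either procedure, while SDAR families return as pain improves. If PDAR families comply, a difference in natural recovery between the operations passes largely into the days saved. Someone advising hernia families could then be given a figure driven mainly by appendectomy, or the reverse.

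**Working it through.** The documents give no figure to reproduce. Every input below is assumed, to show the mechanism and its range.

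**Inputs.** h = share of hernia repairs: 0.2, 0.5, 0.8. SDAR chosen by 80% after hernia repair and 50% after appendectomy. True saving with SDAR: 6 days after hernia repair, 2 after appendectomy.

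**1. Preference share** = 0.8h + 0.5(1 − h).

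- h = 0.2: 0.16 + 0.40 = 56%
- h = 0.5: 0.40 + 0.25 = 65%
- h = 0.8: 0.64 + 0.10 = 74%

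With the same preference in both operations, say 50% and 50%, the share is 50% at every h. At 70% and 50% it runs from 54% to 66%.

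**2. Operation mix within each arm.** The hernia share in SDAR is wS = 0.8h / [0.8h + 0.5(1 − h)]. In PDAR it is wC = 0.2h / [0.2h + 0.5(1 − h)].

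- h = 0.2: wS = 0.16/0.56 = 0.286; wC = 0.04/0.44 = 0.091
- h = 0.5: wS = 0.40/0.65 = 0.615; wC = 0.10/0.35 = 0.286
- h = 0.8: wS = 0.64/0.74 = 0.865; wC = 0.16/0.26 = 0.615

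**3. Unadjusted difference in mean days, equal PDAR means.** The saving is 6wS + 2(1 − wS) = 2 + 4wS. The case-mix average would be 6h + 2(1 − h).

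| h | Unadjusted saving | Case-mix average |
|---|---|---|
| 0.2 | 3.1 | 2.8 |
| 0.5 | 4.5 | 4.0 |
| 0.8 | 5.5 | 5.2 |

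The two columns agree only if families choose SDAR equally often after both operations.

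**4. Unadjusted difference, unequal PDAR means.** Let PDAR recovery be 4 days longer after appendectomy. The apparent saving rises by 4(wS − wC).

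- Savings of 6 and 2 days, h = 0.8: 5.46 + 4 × 0.249 = 6.5 days, above both true values.
- Saving of 3 days in both operations, h = 0.5: 3 + 4 × 0.330 = 4.3 days.
- No saving in either operation, h = 0.5: 0 + 4 × 0.330 = 1.3 days.

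The bias reverses if preferences reverse. At h = 0.5 with SDAR chosen by 40% after hernia repair and 80% after appendectomy, wS = 0.333 and wC = 0.75. A true saving of 3 days in both operations then appears as 3 − 4 × 0.417 = 1.3 days.

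**5. Cost in precision.** With equal outcome SD, the variance of an arm difference is proportional to 1/[n p(1 − p)], where p is the SDAR share. At h = 0.5 the pooled p(1 − p) is 0.65 × 0.35 = 0.2275.

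- Hernia repair, h = 0.5: √[0.2275 / (0.5 × 0.16)] = 1.7 times the pooled interval width
- Appendectomy, h = 0.5: √[0.2275 / (0.5 × 0.25)] = 1.35 times
- Hernia repair, h = 0.2: √[0.2464 / (0.2 × 0.16)] = 2.8 times, where 0.2464 = 0.56 × 0.44

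For the preference share, halving the number of children gives √2 = 1.4 times. With the assumed shares the factor is √(0.32/0.2275) = 1.2 for hernia repair and √(0.50/0.2275) = 1.5 for appendectomy.

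**The case against.** The strongest reply is that the plan does not say the operations will be pooled. Statistical Analysis is a generic list of tests, and nothing in it rules out tables by operation. A reader might infer that the sponsor has committed to one pooled figure. The text does not support that; it supports only that no result by operation is specified. The point survives in that form, because a split first chosen after the data are seen carries less weight. The protocol describes enrolment as still open, although it also calls its results preliminary.

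Second, the aims are broad. The Summary speaks of family preferences after routine surgeries, and both operations share one set of instructions. An overall preference among enrolled children is a legitimate descriptive target. That stands, and it is why an overall figure can be kept. It still needs a stated mix to be usable elsewhere.

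Third, for the arm difference this overlaps with confounding by operation, and stratifying serves both. That also stands. Only the preference share is wholly separate.

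Fourth, every number above is assumed, and pooling does no harm if preference and effect are the same in both operations. This is correct, but results by operation are what would show it.

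A reader might also see this as a contrast between elective and emergency surgery. The documents do not use those terms; they support only two operations with different age ranges.

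**Conclusion.** The point holds as a gap in specified reporting, and one the sponsor should close. Followed as written, the plan gives an SDAR share that depends on the operations enrolled: 56% to 74% under assumed shares of 80% and 50%, and no movement if the shares are equal. It also gives an arm difference that is not a case-mix average once preference differs by operation: 3.1 to 5.5 days for assumed savings of 6 and 2 with equal PDAR means. With unequal PDAR recovery the difference can lie outside both true values. The day figures refer to a difference in means; a Mann-Whitney test does not estimate an average of days saved.

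Two stronger readings are not supported. A reader might infer that the operations do differ in preference or benefit, but the documents give no data by operation, so the size of the problem is unknown. A reader might also infer that the pooled comparison must be dropped. It can stay, provided it is not the only result and the overall estimate takes account of operation.

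**What to change.** Add to Statistical Analysis, before the final analysis:

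1. Report the SDAR share with a 95% interval separately for hernia repair and appendectomy. Give any overall share with the enrolled mix beside it.
2. Report the SDAR-PDAR difference in days to full activity with a 95% interval separately for each operation.
3. Give any overall arm difference as an operation-stratified estimate standardised to a stated case mix. At 50:50 the illustration gives 0.5 × 6 + 0.5 × 2 = 4.0 days, whichever arm families prefer. Use mean differences for this step, since medians do not average across strata.
4. Report the arm-by-operation difference with its interval, labelled exploratory.

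The cost is a few lines of text and one table. Eligibility is defined by operation, so it is known for every child and no new data are needed. The price is precision: the widths in step 5 of the working apply, they are worse for the less common operation, and the arm-by-operation difference will be less precise still. With no stated sample size, the sponsor should expect that the results by operation may be inconclusive. Stratifying by operation also leaves other differences between families who chose different arms untouched.

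### Surgeon is neither recorded nor adjusted for, although several surgeons feed self-chosen arms; if surgeon affects both arm choice and return day, the primary comparison is confounded (minor)

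*Combined protocol and SAP*

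**What the plan says.** **Recruitment.** In Methods, Participants, the source population is "Patients who presented to Beaumont Royal Oak and Beaumont Troy" for one of the two procedures. Eligible children "were identified by the pediatric surgeons, including the Primary Investigator". Families "were provided with an information sheet detailing the study, which served as consent for participation", and those who took part then picked their own arm. There is no randomisation.

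**Surgeon variation.** Background and Significance states "PAR are physician-dependent as evidence-based guidelines for restrictions following routine pediatric surgery are not established". It adds, for exactly the two study procedures, "Recent studies demonstrate considerable variability in surgeons' recommendations following laparoscopic appendectomy and inguinal hernia repair in children".

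**Preference.** Under Objectives: "Secondary outcomes will evaluate patient preference to PDAR and SDAR based on choice of study arm". Nothing other than the chosen arm measures it.

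**Data.** Methods, Data Collection lists baseline characteristics (not itemised), comorbidities, complications, length of stay and pain medication. Surgeon is not named. The survey in Figure 2 does not ask who presented the options.

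**Analysis.** Statistical Analysis says that continuous outcomes are "analyzed using unpaired t tests or Mann Whitney ranked sum tests", and categorical outcomes are given as counts and percentages with chi-square or Fisher tests. There is no surgeon or hospital term. The significance threshold is .05; sidedness is not stated.

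**The concern.** Nothing in the design balances surgeons between the arms. If families seen by one surgeon tend to choose alike, and that surgeon's patients also tend to resume activity earlier or later, part of the arm difference in return day belongs to the surgeon. The planned tests would attribute it to the type of restriction.

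The preference result has a related weakness. The pooled SDAR share is to be read as what families want. If one surgeon offers the study often, or presents it in a distinctive way, the pooled share partly describes that surgeon's practice. Without a surgeon field, the investigators could neither show this nor rule it out.

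**Working it through.** The plan states no sample size, number of surgeons, expected SDAR share or intraclass correlation (ICC), so there is no figure of its own to reproduce. What follows is illustrative.

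**Assumed inputs.** 5 surgeons, m = 24 families each (120 in all); two-sided 5% test; no true arm effect; outcome ICC ρy = 0.05 or 0.10; surgeon effects on choice and on return day independent of each other.

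**1. Choice ICC (ρx).** This is the variance of surgeons' SDAR shares divided by p(1 − p).
- Modest variation: ρx = 0.05 is assumed.
- Shares of 10%, 30%, 50%, 70% and 90%: variance = (0.16 + 0.04 + 0 + 0.04 + 0.16)/5 = 0.08, so ρx = 0.08/0.25 = 0.32 (0.40 with divisor 4). That is six to eight times the modest value.

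**2. Primary test.** The true variance of the arm difference, relative to what the t test assumes, is about V = 1 + (m − 1)·ρx·ρy. Actual rejection is about 2[1 − Φ(1.96/√V)].

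| ρx | ρy | V | Formula | Simulation |
|---|---|---|---|---|
| 0.05 | 0.05 | 1 + 23×0.05×0.05 = 1.058 | 5.7% | 5.5% |
| 0.05 | 0.10 | 1 + 23×0.05×0.10 = 1.115 | 6.3% | 6.1-6.3% |
| 0.32 | 0.05 | 1 + 23×0.32×0.05 = 1.368 | 9.4% | 8.7-9.3% |
| 0.32 | 0.10 | 1 + 23×0.32×0.10 = 1.736 | 13.7% | 13.0-14.1% |

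The simulation ranges cover separate runs of the t test. Mann-Whitney gave 8.4% and 12.9% in the last two rows. If either ICC is zero, V = 1; simulation with 100 families and 5 surgeons gave 5.0% (surgeon affects choice only) and 5.2% (outcome only). Surgeon fixed effects gave 4.2-5.1%.

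**3. Related surgeon effects.** If surgeons whose families favour SDAR also have systematically earlier or later returns, the formula understates the problem. With 100 families and 5 surgeons, a correlation of 0.5 between the two effects gave 5.5-8.8% (ICCs 0.05-0.10). A correlation of 1, with both ICCs at 0.10, gave 16.6%. This is bias, which a variance correction alone would not remove.

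**4. Preference share.** The answer depends on the target.
- *These surgeons, taken as fixed.* An ordinary interval is not too narrow. With shares of 10-90%, the mean of p(1 − p) is (0.09 + 0.21 + 0.25 + 0.21 + 0.09)/5 = 0.17, below the binomial 0.25. Simulated coverage of a 95% Wilson interval was 98.0%, and 95.4% with shares of 44-74%.
- *Surgeons as a random sample of a wider group.* With ICC 0.054, the design effect is 1 + 23×0.054 = 2.2, and coverage falls to about 80%.

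**The case against.** The strongest reply is that the documents contain no mechanism. Surgeons are said to identify patients, not to advise them on the arm. The remark that restrictions depend on the physician describes the field. Inside the study each arm has one set of instructions, which narrows the room for surgeon variation. The information sheet is not in the documents, so neutral presentation cannot be excluded. All of this stands.

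Three stronger readings are therefore tempting but unsupported.
- A reader might infer that the SDAR share does measure surgeons. The documents show only that it could.
- A reader might infer that its precision is overstated. The plan reports a count and a percentage, with no interval, so no precision is claimed; and for these surgeons' own families an ordinary interval would be adequate.
- A reader might infer that the primary test rejects too often. That requires surgeon to affect both choice and outcome, which no section states. The larger inflation figures need extreme share differences or closely related surgeon effects.

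It is also fair to say that the operating surgeon is probably recoverable from the operative record, and that family self-selection is the larger and more certain confounder. Randomising within surgeon is no remedy for the preference outcome, which exists only because families choose.

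What survives is that the plan names surgeon as a source of variation in activity advice, then neither records nor adjusts for it.

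**Conclusion.** The point holds in conditional form and is minor. Surgeon influence on arm choice is neither measured nor controlled. If surgeon affects both choice and return day, the primary comparison is confounded by surgeon, and the pooled SDAR share may partly reflect who offered the study. With modest variation between surgeons and unrelated effects, the excess over 5% is about half to just over one percentage point. It reaches 4 to 9 points when shares run from 10% to 90%, and there is essentially none if surgeon matters for only one of the two. These sizes rest wholly on the assumed number of surgeons, families and ICCs. The case for acting is that the possible bias is cheap to remove, not that it has been shown to be large.

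**What to change.** While enrolment is open:

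1. Record in REDCap the operating surgeon, the person who offered the study, and the hospital. The second is the hardest to reconstruct later.
2. Report the SDAR share by surgeon and by hospital beside the pooled share. State that the pooled share describes these surgeons' families, and that generalising to other surgeons needs a wider interval.
3. Add a surgeon-adjusted comparison of time to full activity: surgeon fixed effects, or a rank test stratified by surgeon. Do not rely on sandwich standard errors with few surgeons.

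**Cost.** A few data fields and one model term or stratum. A surgeon whose families all choose the same arm adds nothing to the within-surgeon comparison, so some information is lost. Adjusting for surgeon does not remove confounding by family self-selection, and the report should say so.

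### The protocol text does not say whether families choose their arm before or after the operation, and it records neither the time of choice nor the child's status then, so selection on early recovery could not be detected or adjusted for

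*Combined protocol and SAP*

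**What the plan says.** The Summary (Study Design) makes allocation a family decision: "Participating families will choose to enroll in either the control (PDAR) or experimental (SDAR) groups". Methods, Participants, gives the only sequence: the surgeons identify an eligible child, the family receives an information sheet that serves as consent, and then "Parents and patients who elected to participate then chose to enroll in the control group (PDAR) or experimental group (SDAR". The operation does not appear in that sequence.

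Two indirect cues point in different directions:
- Entry is defined by "Patients who presented to Beaumont Royal Oak and Beaumont Troy for a routine inguinal hernia repair (ages 2-13 years) or laparoscopic appendectomy", which suggests an approach before surgery but describes eligibility, not the moment of choice.
- The survey (Figure 2) asks "Were you satisfied with the instructions detailed in your discharge guidelines", which fits instructions handed over after surgery but does not date the choice either.

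The SDAR instruction is that "they may return to full activity when their pain is improving and the parent, or guardian, feels comfortable advancing their activity". Under PDAR, "patients are restricted from full, normal activity for 2 weeks after their procedure".

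On data, the plan states: "Baseline characteristics, comorbidities, surgical complications, length of stay, and pain medications will be obtained for each participant from the time of surgery". Neither the time of arm choice nor pain at choice is listed. The primary outcome (Objectives) is time to full activity, which the survey asks for in days after surgery. Statistical Analysis provides only two-group tests: an unpaired t test or a Mann-Whitney test for continuous data.

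**The concern.** In a family-choice design, confounding by age, procedure and family attitude is expected. This is a further path. The outcome clock starts at surgery, so if the arm is chosen after surgery, the choice can rest on an early reading of the outcome itself. SDAR makes this likelier, because its own condition for resuming activity is improving pain: a family already seeing improvement has a direct reason to prefer it. Adjusting for age and procedure would not remove this, and the plan adjusts for nothing.

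The two procedures may differ in exposure. A planned hernia repair allows a choice beforehand. For appendectomy, eligibility requires uncomplicated disease, which may be settled only at operation; the protocol does not say when it is judged.

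There is a second consequence. Complications and pain medication are collected from surgery onward. Without a choice time, events before the choice cannot be separated from events after it, and could be compared between arms as though the arm had produced them.

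**Working it through.** **No plan figure to reproduce.** The documents give no sample size, power, SD, effect size or allocation ratio. What follows shows direction and possible size only.

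**What the text fixes.** Choice by family (Summary; Participants); no stated time of choice (Participants); outcome counted from surgery (Figure 2); unadjusted tests at .05 (Statistical Analysis).

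**Assumptions.** SD of time to full activity 5 days; equal arms; no true effect of the instruction; early recovery seen by the family correlates ρ with the outcome and r with the arm actually chosen.

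**Formula.** With equal arms, a correlation r with a two-valued arm means the arms differ by r/0.5 = 2r SD in early recovery. A fraction ρ of that carries over to the outcome, so

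spurious difference = 2 × ρ × r × SD.

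- ρ = 0.3, r = 0.3: 2 × 0.3 × 0.3 = 0.18 SD; × 5 = 0.9 day.
- ρ = 0.5, r = 0.5: 2 × 0.5 × 0.5 = 0.50 SD; × 5 = 2.5 days.

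**Allowing for the PDAR restriction.** If compliance holds PDAR times near two weeks whatever the early recovery, only the SDAR mean moves, by ρ × r × SD: 0.3 × 0.3 × 5 = 0.45 day, and 0.5 × 0.5 × 5 = 1.25 days.

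**Cross-check with another choice model.** Let the odds of choosing SDAR rise by a factor OR per SD of faster early recovery, again with no true effect and about equal arms. Simulated spurious differences, in SD units:

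| ρ | OR 1.5 | OR 2 | OR 3 |
|---|---|---|---|
| 0.3 | 0.12 | 0.19 | 0.27 |
| 0.5 | 0.20 | 0.31 | 0.44 |
| 0.7 | 0.27 | 0.44 | 0.62 |

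At SD 5 this spans about 0.12 × 5 = 0.6 day to 0.62 × 5 = 3.1 days. The two models agree. At ρ = 0.5 the formula gives a difference of 2 × 0.5 × r = r SD, so OR 2 corresponds to r of about 0.31 and OR 3 to about 0.44. An r of 0.5 is therefore stronger selection than any simulated setting, and the 2.5-day figure is a strong case.

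**If choice cannot depend on recovery (OR = 1).** The difference is 0.00 SD, and both tests reject 4.1% to 5.5% of the time, close to nominal. This describes a choice made before the operation. It does not carry over to choices made after it.

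**The case against.** The strongest reply is that silence is not a flaw shown. Figure 1 and the information sheet are not in the supplied text, and either could say when families choose. Presenting for an operation, then being identified, informed and asked to choose, reads quite naturally as enrolment before surgery. No passage says that uncomplicated appendicitis is established only at operation. This stands: the finding must be limited to what the supplied text does not state. A reader might infer that families did choose SDAR after watching a child recover. The documents permit that but do not show it for any family.

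Second, every numerical input is assumed, and the no-effect setting is unrealistic, since a two-week restriction should itself lengthen PDAR times. This also stands. A false-positive rate under equality is not the relevant measure here; the issue is a bias that adds to an expected difference and cannot be separated from it.

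Third, this is one path within a larger self-selection problem, and dating the choice leaves the rest untouched. True, but this path needs its own data. If time of choice and status at choice are not captured, no later analysis can recover them.

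**Conclusion.** The gap holds as a gap in the supplied protocol text: the arm choice is not placed before or after surgery, and neither its time nor the child's status at choice is listed for collection. Where the choice follows surgery, the planned comparison would attribute prior good recovery to SDAR, on top of ordinary self-selection and of the difference expected from the PDAR restriction.

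Under the stated assumptions the added difference is about 0.9 day in a moderate case and 2.5 days in a strong one, or about half that if PDAR times are held near two weeks. These show direction and range and are not estimates for this trial.

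Two stronger readings are not supported. One is that the trial's SDAR advantage, if found, is an artefact of late choice: if every choice was made before surgery, this mechanism does not operate. The other is that fixing the choice point would make the comparison unbiased: the arms would still be self-selected. The point deserves an amendment because the protocol says enrolment is still accruing and the remedy is cheap.

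**What to change.** For children still to be enrolled:

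1. Take and lock the arm choice before surgery for planned inguinal hernia repair. For appendectomy, take it before surgery where eligibility can be judged then; otherwise at one fixed, earliest point after uncomplicated appendicitis is confirmed.
2. Record the date and time of choice and one caregiver pain rating at that moment.
3. Prespecify a regression of time to full activity on arm, adjusted for procedure, age, timing of choice (before or after surgery) and, for choices after surgery, pain at choice. Add a sensitivity analysis restricted to choices made before surgery.
4. Do not count events recorded before the choice as outcomes of the arm.

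For children already enrolled, use a choice date only if one was recorded; otherwise report the timing as unknown. If the information sheet or Figure 1 already fixes the time, state it in Methods and keep items 2 to 4.

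The cost is a few enrolment fields and a short amendment; neither activity instruction changes. The limits should be stated openly: bias for appendectomy is reduced but not removed, preoperative confounding remains, and the sensitivity analysis will consist mostly of hernia repairs, so it says least about the procedure where a choice after surgery is most plausible.
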